28.0 Study Plan - Details

28.1 Research Methods - Include the Schedule of Events or provide a precise description of the data collection methods. (Attach the Schedule of Events to the Initial Review Submission Form, if applicable)

Overview of Study Design.

A total of 50 subjects per study will be randomly assigned to double-blind, subchronic dosing with active drug (n = 25) or matched placebo (n = 25). Subjects will meet the Diagnostic and Statistical Manual – 5th Edition (DSM V) criteria for alcohol use disorder of at least moderate severity (AUD-MS) and be non-treatment-seeking, to avoid exposing treatment-seeking individuals with AUD-MS to alcohol cues. Alcohol abstinence is required during the last 3 days of the dosing period in order to test the effect of study drug when motivational symptoms of early abstinence are manifest. Human lab testing occurs on the last day of dosing/third day of abstinence.

Subjects are presented with 12 positive, negative or neutral affective images selected from the International Affective Picture System on a flatscreen monitor (IAPS). Each affective condition is followed by in vivo exposure to the subject's preferred alcoholic beverage or bottled water, which the subject is told to view and smell for 90 seconds and to not drink it. Endpoints selected assess the effects of drug relative to placebo on responsivity to in vivo alcohol cue exposure in the lab, as well as on naturalistic measures of drinking, affect, and craving through 1-month posttreatment.

These methods inform the 3 stages of the addiction cycle: preoccupation/anticipation (craving), binge/intoxication (drinking quantity and frequency, binge drinking) and negative affect (mood, anxiety). Craving in response to alcohol cue exposure in the lab has been reliably predictive of subsequent drinking in alcoholics, and thus craving in response to in vivo alcohol cue exposure in the laboratory comprises the primary outcome for this proof-of-concept study. Self-reported drinking data are collected as a secondary outcome variable, as the 3-day abstinent interval constrains complete evaluation of this variable, and drinking data are collected under less

controlled conditions than craving in response to in vivo alcohol cue exposure in the lab.

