Subjects return 1 week and 1-month after drug discontinuation to assess any persisting effects on naturalistic measures of drinking, craving and affect. A positive signal on such indices would lend support to the potential utility of the drug in the treatment of AUD-MS and identify endpoints likely to show a positive drug effect in clinical trials.

Study Procedures:

Visit 1-Screening: After providing written informed consent, subjects complete the Screening Visit for initial evaluation of eligibility. A mini-cue session familiarizes subjects with the human lab setting and identifies non- cue-reactive subjects for study exclusion (Visual Analogue Scale [VAS] craving rating of alcohol cue < 3 points higher than water cue).

Visit 2-Randomization: Subjects complete the evaluation for eligibility. Medically cleared subjects complete baseline assessments and are randomized to receive a blistercard containing the double-blind study drug. A phone call is scheduled for Day 3 (and Day 7 in studies having 8-10 days of drug exposure) to address any questions or concerns and assess compliance.

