NCT03175549

Medication Development in Alcoholism: Apremilast versus Placebo

Statistical Analysis Plan Date: 01/20/2017

Statistical Analysis Plan, Demographic and baseline clinical characteristics will be examined for group differences by Fisher's Exact test for categorical/dichotomous variables and ANOVA for continuous variables. Variables will be tested individually for correlation to each outcome variable by Pearson's product-moment correlation or χ^2 , as appropriate. Any variable significantly associated with outcome or differing between treatment groups will be evaluated in all subsequent analyses as a covariate and will be retained if it reduces the residual variance, or otherwise will be left out of the model. Potential covariates of interest include baseline value of a measure, baseline values of peripheral markers of inflammation and stress response, sex. family history of alcoholism, smoking, and age of onset of heavy drinking. 98,99,100 Hypothesis: Subjects treated with active drug (apremilast) will report significantly lower VAS craving ratings in response to in vivo alcohol cues during human lab testing than placebo treated subjects. Repeated measures mixed effects models (MEM)¹⁰¹ will be used to examine drugplacebo differences in VAS craving ratings in response to beverage exposure (alcohol vs. water), where drug is treated as a fixed, between-subjects variable and beverage presentation is the repeat measure. Beverage will be considered a fixed, within-subjects variable and subject as a random effect. Drug effects on naturalistic secondary outcomes, i.e., drinking, will be examined using repeat MEM, as above Safety evaluations: Rates of treatment-emergent signs and symptoms will be computed for each treatment group by body system (e.g., liver, hematologic). Changes and trends in laboratory results will be examined based on shift tables and scatter plots. Relationship to exposure (dose and time) to study drug will be examined. χ^2 analyses will be used to compare the drug groups on rate of study discontinuation due to adverse reactions and overall.

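### Read literally, the primary craving model pools the alcohol-cue and water-cue variances, so a drug contrast at the alcohol cue has the wrong standard error if those variances differ

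*SAP*

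**What the plan says.** The SAP's hypothesis is that apremilast subjects "will report significantly lower VAS craving ratings in response to in vivo alcohol cues during human lab testing than placebo treated subjects". Protocol section 28.1 (Overview of Study Design) agrees: "craving in response to in vivo alcohol cue exposure in the laboratory comprises the primary outcome".

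The SAP analyses the alcohol and water ratings jointly in a repeated measures mixed effects model, "where drug is treated as a fixed, between-subjects variable and beverage presentation is the repeat measure". It adds: "Beverage will be considered a fixed, within-subjects variable and subject as a random effect". The text gives no residual covariance structure, beverage-specific variance, robust standard error or degrees-of-freedom method. It also does not say which term is the test: the drug main effect, the drug-by-beverage interaction, or the drug difference at the alcohol cue.

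Protocol section 28.1 (Visit 3) describes six ratings per subject, from three affect conditions crossed with two beverages. The SAP model names beverage but not affect, and does not say whether the six ratings are averaged. Neither document gives an SD or a correlation for the VAS ratings.

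**The concern.** A model whose only random term is a subject intercept, with a single residual variance, gives alcohol and water ratings the same total variance. The hypothesis as worded concerns one of the two cues. Its contrast would therefore borrow half its variance estimate from ratings at the other cue.

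There is a plausible reason for the variances to differ. At Visit 1 subjects are excluded as non-cue-reactive if they have a VAS "craving rating of alcohol cue < 3 points higher than water cue". Enrolled subjects therefore rate water well below alcohol at screening. If water ratings crowd the bottom of the scale they will vary less, and pooling then makes the alcohol-cue standard error too small. In a trial of 25 versus 25, the primary confidence interval would be too narrow and the false-positive rate above its nominal level. The alcohol-cue contrast and the interaction could also disagree for a purely technical reason.

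**Working it through.** **Inputs.** From the documents: 25 per arm (protocol 28.1), drug and beverage fixed, subject random (SAP). Assumed because not stated: two-sided 5% level, one averaged rating per beverage, and a range for q = (water SD)/(alcohol SD). The plan states no error rate or power for this model, so there is no figure of its own to reproduce.

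**What the literal model estimates.** Let the variances be σA² (alcohol) and σW² (water), with covariance c within subject. In the balanced two-rating random-intercept model:

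- expected between-subject mean square = (σA² + σW² + 2c)/2
- expected within-subject mean square = (σA² + σW² − 2c)/2
- model variance of a single rating = average of the two = (σA² + σW²)/2

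The covariance cancels, so the correlation hardly matters. The true variance of the drug difference at the alcohol cue is (2/25)σA², but the model uses (2/25)(σA² + σW²)/2.

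**Size of the error.** Model SE / true SE = f = √((1 + q²)/2), and the large-sample type I error is 2[1 − Φ(1.96 f)].

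| q (water SD / alcohol SD) | f | 1.96 f | type I error |
|---|---|---|---|
| 1.25 | √1.281 = 1.132 | 2.219 | about 2.7% |
| 1.0 | 1.000 | 1.960 | 5.0% |
| 0.9 | √0.905 = 0.951 | 1.865 | 6.2% |
| 0.8 | √0.820 = 0.906 | 1.775 | 7.6% |
| 0.5 | √0.625 = 0.791 | 1.550 | 12.1% |

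**Finite-sample check.** Simulation with 25 per arm, correlations 0.2, 0.5 and 0.8, Satterthwaite degrees of freedom and 40,000 trials per setting gave 2.6–2.7% at q = 1.25, 4.9–5.1% at 1.0, 7.2–7.6% at 0.8 and 11.5–12.0% at 0.5. In the same simulations:

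- with the alcohol-cue contrast judged on its own variance, type I error was 4.7–5.2% at every ratio tried
- the drug-by-beverage interaction and the drug main effect stayed at 4.8–5.3% throughout, because for these two contrasts the relevant mean square is the correct one

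**If all six ratings are fitted with subject as the only random effect.** At q = 0.5 the alcohol-cue test runs at about 13–17%. It is about 6–7% even at q = 1 if ratings of the same beverage correlate more within a subject than ratings of different beverages. The interaction then loses its protection too: it is about 12–13% at q = 0.5 when all ratings correlate at 0.6 within subject, and higher with extra same-beverage correlation.

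**Cost of separate variances when they are in fact equal.** The alcohol-cue contrast moves from up to 96 to 48 denominator degrees of freedom. The critical t moves from 1.985 to 2.011, a ratio of 1.013. At an assumed standardised difference of 0.8 and 25 per arm (noncentrality 0.8 × √12.5 = 2.83), power falls from 80.0% to 79.1%.

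**The case against.** A reader might infer that the SAP prescribes a wrong model and that the primary test has a false-positive rate well above 5%. The documents do not support that, for four reasons.

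1. The SAP does not state a common variance. A repeated measures mixed model with an unstructured or heterogeneous covariance is compatible with its text, and it cites a methods reference that is not reproduced. This stands: the common variance is the literal reading of a sentence that names only a subject effect, not a declared assumption.
2. The SAP does not name the tested term. Its analysis sentence, comparing drug with placebo across alcohol and water, fits the interaction as well as the alcohol-cue contrast, and the interaction on averaged ratings is sound. This also stands, although the hypothesis and the protocol's primary outcome both point to the alcohol cue.
3. The direction of any bias is undocumented. The screening rule limits a difference, not a variance. With equal variances and joint normality, selecting on that difference would shrink both variances equally. A floor for water is plausible, but a ceiling for alcohol would work the other way, and the VAS range is not given. With covariates in the model, the residual SDs are what count.
4. The averaged-rating figures presume averaging that the SAP does not describe, and a 2x2 covariance does not define a model for six ratings. The change must therefore include the averaging step.

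What the objection does not remove is that an analyst following the SAP as written would most naturally fit a random intercept, and nothing in the text protects the contrast that the hypothesis names.

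**Conclusion.** The point holds conditionally. If the SAP is fitted as literally written, if the test is the drug difference at the alcohol cue, and if the two cue variances differ, the standard error is wrong. With averaged ratings, the type I error is about 7.6% at a water/alcohol SD ratio of 0.8 and about 12% at 0.5. It is nominal at 1.0 and conservative, at about 2.7%, at 1.25. The ratio and the 5% level are assumptions, so these figures show sensitivity and do not forecast the trial's error rate. The gap is in specification, but it concerns the primary analysis of a 50-subject trial, and closing it costs almost nothing.

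**What to change.** In the SAP:

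- Name the drug difference in VAS craving at the alcohol cue as the tested contrast, with drug-by-beverage as supporting.
- State that the three affect-condition ratings are averaged to one alcohol and one water value per subject.
- Replace the subject-only random intercept with an unstructured 2x2 within-subject covariance (two variances and a covariance) and Kenward-Roger degrees of freedom. Take both contrasts from that fit.
- If all six ratings are modelled instead, allow beverage-specific subject effects and beverage-specific residual variances.

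The cost is a few sentences, one extra covariance parameter and fewer denominator degrees of freedom (48 instead of up to 96). If the variances are equal, the power loss is negligible (under one percentage point in the case worked above). No new data or visits are needed.
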